STATISTIC

The results obtained from clinical, instrumental and subjective evaluations will be compared between experimental timepoints and later between treatments.

The hypothesis tests used in the study will have a 95% significance level and the statistical power of these tests will be above 80%.

➤ Study Variables

Primary Variables

- To evaluate the treatment superiority with the Exímia Probiac® product associated with the Epiduo® product use versus placebo use and Epiduo® on the success rate of the participants percentage with a reduction in the total number of inflammatory and non-inflammatory lesions in the facial region.
- To evaluate the treatment superiority with the Exímia Probiac® product associated with the Epiduo® product use versus placebo use and Epiduo® on the success rate of the participants percentage with regression of the IGA scale score to grade 1 or zero.

Secondary Variables

- To compare the treatment with the Exímia Probiac® product associated with the Epiduo® product use versus placebo use and Epiduo® on the response rate of the individuals percentage who had regression of the IGA scale score.
- To compare the treatment with the Exímia Probiac® product associated with the Epiduo® product use versus placebo use and Epiduo® on the perceived efficacy of the volunteer, evaluated through subjective questionnaires.
- To compare the treatment with the Exímia Probiac® product associated with the Epiduo® product use versus placebo use and Epiduo® on the evaluation of dilated pores and inflammatory lesions through photographic records and analysis of the Visia® equipment software.

➤ Statistical Methodology

• Primary Variables data analysis

First, we will perform descriptive analyses of the study variables through frequency tables and descriptive statistics (means, standard deviation, minimum, maximum and quartiles).

The percentage of participants with a reduction in the total number of inflammatory and non-inflammatory lesions, the percentage of participants with regression of the IGA scale score to cured (zero score) or almost cured (score one) will be evaluated through the *z test* for comparison of two proportions. The tested hypotheses will be:

$$H_0: \text{Perci}(P + E) \leq \text{Perci}(E)$$

$$H_a: \text{Perci}(P + E) > \text{Perci}(E)$$

Where Percc is the percentage of participants for each study variable.

• Secondary Variables data analysis

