In order to evaluate the individuals percentage who presented regression of the IGA scale score, primarily a data descriptive analysis will be performed and subsequently the evaluation through the z test for two proportions.

Ho: $\text{Perci}(P + E) \leq \text{Perci}(E)$

Ha: $\text{Perci}(P + E) > \text{Perci}(E)$

Where Percc is the percentage of participants for each study variable.

The comparison between treatments of perceived efficacy evaluated through a subjective questionnaire and counting the number of inflammatory lesions and dilated pores will be carried out using the Mann Whitney test, which is the most suitable for evaluating ordinal data from independent samples. The tested hypotheses will be:

Ho: $\text{Medj}(P + E) = \text{Medj}(E)$

Ha: $\text{Medj}(P + E) \neq \text{Medj}(E)$

Where Medj is the median of the results of each study variable.

The results will be considered statistically significant at a significance level of 5% (P value ≤ 0.05). The significance level will be controlled by rejecting the null hypotheses if the p Value is less than or equal to 5%.

For the analysis of pores and inflammatory lesions through the Visia® equipment, the equipment's raw data will be exported regarding the parameters quantification of each participant in their respective experimental time. The Anderson-Darling normality test will be applied to identify the data normality. According to the samples distribution result, it will be checked whether there is a difference between the experimental timepoints:

- Parametric tests - *t-student* for paired data to compare experimental timepoints if the normality hypothesis is not rejected;
- Nonparametric tests - *Wilcoxon* for paired data to compare experimental timepoints and *Mann-Whitney*, in case normality is rejected.

Subsequently, the results will be compared between experimental timepoints and later between treatments.

The results will be considered statistically significant at a 5% significance level (P value ≤ 0.05). The significance level will be controlled by rejecting the null hypotheses if the p Value is less than or equal to 5%.

The data collected in the studies will be evaluated according to the statistical methodology described and primary and secondary study variables, after the participants return from D60, D90 visits and the final visit D180.

➤ Sample Design

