The study primary hypothesis is the superiority of the Exímia Probiac® and Epiduo® (P + E) combination in relation to Epiduo (E) in the mean percentage change in the number of inflammatory lesions and in the mean percentage change in non-inflammatory lesions. Below is a sample size calculation for the superiority hypotheses: The hypotheses tested for the superiority study will be:

$$H_0: p_t - p_c \leq \delta$$

$$H_A: p_t - p_c > \delta$$

The sample size in each group was calculated considering the following formula:

$$n = \frac{(p_t(1-p_t) + p_c(1-p_c)) (z_{1-\alpha/2} + z_{\beta})^2}{(p_t - p_c - \delta)^2}$$

Where:

For a 5% significance level

$z_{\beta} = 0,864$ → for 80% test power

p_t is the expected proportion of the test group, 69.23%

p_c is the expected proportion of the control group, 52.50%

δ is the margin of superiority, where we will use 1%

Considering the parameters, the sample size considered in the study will be of 200 participants in each group, totaling 400 participants.

➤ Randomization of treatments

The participant determination who will be part of each treatment is performed randomly.

The codes of the 400 participants were arranged in a column in the MINITAB statistical program, then a random sample of 200 participants was selected. Selected participants will use the Probiac and Epiduo combination and the remaining participants will use Placebo and Epiduo.

To ensure that the study is double-blind, the identification that the participant will receive each product sample will be performed by the sponsor according to the study randomization. The collaborators/research assistants who have contact with the participants, during the execution and dispensing of the products to the participants, do not have access to the type of product being used.

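### The primary variables are tested at D60, D90 and D180, each at an unadjusted 5%, and no visit is named as decisive, so the 5% level does not hold for a superiority claim on a primary variable

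*SAP*

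**What the plan says.** The SAP defines two primary variables under Study Variables: a success rate based on lesion reduction, and superiority "on the success rate of the participants percentage with regression of the IGA scale score to grade 1 or zero". Under Primary Variables data analysis each is assigned a z test "for comparison of two proportions. The tested hypotheses will be" one-sided, in favour of the combination.

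On timing, the last paragraph of Statistical Methodology says that the data "will be evaluated according to the statistical methodology described and primary and secondary study variables", and that this happens "after the participants return from D60, D90 visits and the final visit D180".

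On error control, the text on secondary variables and on the Visia® analysis gives a per-test rule: "The results will be considered statistically significant at a 5% significance level (P value ≤ 0.05"), followed by "The significance level will be controlled by rejecting the null hypotheses if the p Value is less than or equal to 5" per cent. The opening Statistic section sets a single level for the study's hypothesis tests (printed as 95%, evidently the confidence level).

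Neither primary variable, nor its hypotheses, nor the Sample Design section carries a visit. D180 is called the final visit, not the primary one. The SAP has no multiplicity adjustment, testing order or division of alpha, and nothing says that D60 and D90 are descriptive.

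**The concern.** A rule that compares each p-value with 5% controls the error of one test. It does not control the error of a claim that may rest on any of three tests of the same variable. As the SAP stands, a significant z test at D60, D90 or D180 would each meet its criterion for superiority on a primary variable, and a reader of the results could not tell which visit had been meant to decide. Once results have been seen, naming the visit is no longer credible, so this has to be settled beforehand.

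**Working it through.** **The plan's own figure.** Sample Design is written for one comparison of two proportions at no stated visit. Its inputs are 69.23% and 52.50%, margin 1%, z(1−α/2) = 1.960 and z_β = 0.864.

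- Variance term: 0.6923 × 0.3077 + 0.525 × 0.475 = 0.4624
- Effect less margin: 0.6923 − 0.525 − 0.01 = 0.1573
- n = 0.4624 × (1.960 + 0.864)² / 0.1573² = 149.03, so 150 per group

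The stated 200 per group is not reproduced. The difference is on the generous side and does not bear on this point. What matters here is that the calculation budgets for one test, while the closing paragraph of Statistical Methodology runs three per primary variable.

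**False positives, one primary variable, three visits.** Inputs from the SAP: three visits, a one-sided alternative, 5% per test. The SAP gives no between-visit correlation, so ρ is an assumption, taken as equal for all pairs of visits. Under no treatment effect, with c the critical value (1.645 at 5%, 1.960 at 2.5%):

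P(at least one z > c) = 1 − ∫ Φ((c − √ρ·u)/√(1−ρ))³ φ(u) du

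If the three tests were independent, the 5% case would be 1 − 0.95³ = 14.3%.

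| Assumed ρ between visits | One-sided 5% per test | One-sided 2.5% per test |
|---|---|---|
| 0.3 | 13.0% | 6.8% |
| 0.5 | 11.8% | 6.3% |
| 0.7 | 10.3% | 5.5% |
| 0.9 | 8.0% | 4.2% |

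The 2.5% column is shown because the sample-size formula uses α/2 although the tested hypotheses are one-sided. It is to be read against a nominal 2.5%. In both columns the rate exceeds its nominal level at every ρ shown.

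**Both primary variables, if either were enough.** This is a further assumption that the SAP does not state. The correlation between different primaries at different visits is taken as the product of the two correlations. One-sided 5% per test, six tests:

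| ρ between visits | Correlation between primaries 0.3 | Correlation between primaries 0.7 |
|---|---|---|
| 0.3 | 23.1% | 20.1% |
| 0.5 | 21.0% | 18.3% |
| 0.7 | 18.4% | 15.9% |
| 0.9 | 14.4% | 12.4% |

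Part of this excess comes from having two primaries and not from the visits: two independent tests alone would give 1 − 0.95² = 9.75%.

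**What an adjustment would cost in power.** At 200 per group, with the SAP's proportions and its 1% margin, the expected z is 0.1573 / √(0.4624/200) = 3.271.

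- Bonferroni over three visits: 0.05/3 = 0.0167, critical value 2.128, power Φ(1.143) = 87%
- Bonferroni over six tests: 0.05/6 = 0.0083, critical value 2.394, power Φ(0.877) = 81%

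These are powers per test and assume that the planned difference is present at the visit tested.

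**The case against.** **The protocol may name the primary visit.** It is not at hand, and an endpoint's visit is often fixed there. This stands as a caution about the fix. It does not remove the point, because this SAP itself lists three evaluation times and gives its own error rule, and the two do not fit together.

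**The sentences on control are per-test rules.** They sit in the secondary and Visia® text, not under the primary variables, and they do not mention error across visits. That is fair: the SAP does not expressly promise familywise control. But it offers no other rule for the primary variables, so a 5% level for a claim that may come from any visit has nothing behind it.

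**The figures depend on assumptions.** They do: the correlations are assumed, the sidedness is inconsistent within the SAP, and the six-test figures need a win-on-either rule that is not stated. The ranges above show how far each assumption moves the result, and none brings it down to nominal.

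**A stronger reading: early unblinding.** A reader might infer that the SAP schedules comparative looks at D60 and D90 and so endangers the double blind. The text does not establish this. The timing sentence can equally mean one evaluation, covering three visits, once all are complete. No interim look, data cut or release of results is described. Randomization of treatments says that product identification "will be performed by the sponsor according to the study randomization", and that staff in contact with participants do not know the product. It does not say who runs or sees between-arm analyses, and percentages by arm would not by themselves reveal individual allocations. Under the single-analysis reading the early-results question falls away, and the multiplicity across visits remains.

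**Conclusion.** The point holds as a multiplicity defect in the confirmatory analysis. For one primary variable tested one-sided at 5% at three visits, the chance of at least one false positive is about 13% to 8% for assumed between-visit correlations of 0.3 to 0.9. With directional tests at 2.5% it is about 6.8% to 4.2% against 2.5%. The range of about 12% to 23% for two primaries applies only if success on either is enough, and should not be quoted as the trial's error rate without that condition. The calculation assumes normal test statistics, equal correlations between visits, and a claim allowed from any visit. The SAP does not exclude such a claim.

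The SAP does not show that anyone would see comparative results early. On that, the most that can be said is that the timing of the between-arm tests is left open.

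**What to change.** - Name one confirmatory visit for the primary variables. D180, the final visit, is the natural choice unless the protocol already names another, in which case the SAP should repeat that one.
- Label the remaining visits supportive, with estimates and confidence intervals but no superiority claim.
- If another visit is meant to support a claim, give it a stated share of alpha and fix the method in advance. Bonferroni is one option, with the power shown above.
- State whether the directional tests use 5% or 2.5%, and whether success is needed on both primary variables or on either. If either is enough, the alpha must also be divided between them.
- State whether between-arm tests are run once, after the last D180 visit and data lock, or as each visit completes. If the latter, state who sees the results.

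Naming the visit costs a few lines in the SAP and no extra participants. The sponsor gives up unadjusted confirmatory claims at the other visits.
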